## 5.2 Subject Exclusion Criteria

**Subject Exclusion Criteria:** Subjects eligible for this study must not meet any of the following criteria:

1. Life expectancy  $< 4$  months;
2. Subjects with radiographic evidence of central nervous system (CNS) metastases as assessed by computerized tomography (CT) or magnetic resonance imaging (MRI) that are not well controlled (symptomatic or requiring control with continuous corticosteroid therapy [e.g., dexamethasone]). Note: Subjects with CNS metastases are permitted to participate in the study if the CNS metastases are medically well controlled prior to screening (as assessed by the Investigator) after receiving local therapy (irradiation, surgery, etc.);

Protocol: A Phase 2 Open Label, Multi-Center, Multinational Study Investigating The Efficacy and Safety Of GTx-024 On Advanced, Androgen Receptor-Positive Triple Negative Breast Cancer (AR+ TNBC)	Compound No.: GTx-024 Author: [name]
---	---

3. Radiotherapy within 14 days prior to the first dose of study treatment;
4. Have, in the judgment of the Investigator, a clinically significant concurrent illness or psychological, familial, sociological, geographical, or other concomitant condition that would not permit adequate follow-up and compliance with the study protocol;
5. Positive hepatitis B virus (HBV) and/or hepatitis C virus (HCV) infection at screening;
6. Positive human immunodeficiency virus (HIV) infection at screening;
7. Prior treatment with any anti-androgens, including but not limited to, enzalutamide and bicalutamide;
8. Major surgery within 28 days of the first dose of study treatment;
9. Be currently taking or have previously taken testosterone, methyltestosterone, oxandrolone (Oxandrin®), oxymetholone, danazol, fluoxymesterone (Halotestin®), testosterone-like agents (such as dehydroepiandrosterone, androstenedione, and other androgenic compounds, including herbals), or anti-androgens;
10. Treatment with any of the following hormone replacement therapies, unless discontinued at least 28 days prior to the first dose of study treatment:
  - Estrogens
  - Megesterol acetate;
11. Treatment with any investigational agent within 28 days before the first dose of study treatment;
12. Another active cancer (excluding adequately treated basal cell carcinoma or cervical intraepithelial neoplasia [CIN]/cervical carcinoma in situ or melanoma in situ). Prior history of other cancer is allowed as long as there is no active disease within the prior 5 years;
13. Subject has a concomitant medical condition that precludes adequate study treatment compliance or assessment, or increases subject risk, in the opinion of the Investigator, such as but not limited to:
  - Myocardial infarction or arterial thromboembolic events within 6 months prior to baseline or severe or unstable angina, New York Heart Association (NYHA) Class III or IV disease, or a QTcB (corrected according to Bazett's formula) interval > 470 msec; serious uncontrolled cardiac arrhythmia grade II or higher according to NYHA; uncontrolled hypertension (systolic > 150 and/or diastolic > 100 mm Hg)
  - Acute and chronic active infectious disorders and non-malignant medical illnesses that are uncontrolled or whose control may be jeopardized by the complications of this

Protocol: A Phase 2 Open Label, Multi-Center, Multinational Study Investigating The Efficacy and Safety Of GTx-024 On Advanced, Androgen Receptor-Positive Triple Negative Breast Cancer (AR+ TNBC)	Compound No.: GTx-024 Author: [name]
---	---

- study therapy
  - Impairment of gastrointestinal function or gastrointestinal disease that may significantly alter the absorption of study drugs (e.g., ulcerative disease, uncontrolled nausea, vomiting, diarrhea, malabsorption syndrome);
- 14. Current treatment with intravenous bisphosphonate or denosumab with elevated serum calcium corrected for albumin or ionized calcium levels outside institutional normal limits at screening;
- 15. History of non-compliance to medical regimens;
- 16. Subjects unwilling to or unable to comply with the protocol procedures as assessed by the Investigator;
- 17. Concurrent participation in another therapeutic clinical trial.

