## 5 STUDY ENROLLMENT AND WITHDRAWAL

### 5.1 Subject Inclusion Criteria

**Subject Inclusion Criteria:** Subjects eligible for inclusion in this study must meet **all** of the following criteria:

1. Able and willing to give voluntary, written and signed, informed consent;
2. Women  $\geq$  18 years of age;
3. Women with TNBC who have received at least one but no more than two prior chemotherapy regimens for the treatment of advanced or metastatic TNBC;
4. Confirmation of AR+ (defined as  $\geq$  10% nuclear AR staining by immunohistochemistry [IHC]) TNBC in either the primary or metastatic lesion, assessed prior to the start of or during the screening period by a local laboratory or by medical history;
5. TNBC confirmed by medical history as: HER2-negative (confirmed by IHC 0, 1+ regardless of fluorescence in situ hybridization [FISH] ratio; IHC 2+ with FISH ratio lower than 2.0 or *HER2* gene copy less than 6.0; FISH ratio of 0, indicating gene deletion, when positive and negative in situ hybridization [ISH] controls are present); ER negative (confirmed as ER expression less than or equal to 1% positive tumor nuclei); progesterone receptor negative (confirmed as progesterone receptor expression less than or equal to 1% positive tumor nuclei);
6. Availability of paraffin embedded or formalin fixed tumor tissue; OR, a minimum of 10 and up to 20 slides of archived tumor tissue or new biopsy, if archived tissue is unavailable, for central laboratory confirmation of AR status and molecular subtyping. Metastatic tumor tissue is preferred when possible;
7. Subjects must have either measurable disease or bone-only non-measurable disease, according to RECIST 1.1;
8. Subjects with bone metastases should be treated with intravenous bisphosphonates or subcutaneous denosumab (or investigator preferred standard of care) prior to and/or during the trial, unless there is a contraindication or subject intolerance to these therapies. For subjects who are normocalcemic, therapy can be initiated at the time the subject initiates study drug;
9. Eastern Cooperative Oncology Group (ECOG) performance status 0 or 1 at the time of screening and enrollment;

Protocol: A Phase 2 Open Label, Multi-Center, Multinational Study Investigating The Efficacy and Safety Of GTx-024 On Advanced, Androgen Receptor-Positive Triple Negative Breast Cancer (AR+ TNBC)	Compound No.: GTx-024 Author: [name]
---	---

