10. Negative serum pregnancy test in women of childbearing potential (premenopausal or less than 12 months of amenorrhea post-menopause, and who have not undergone surgical sterilization), no more than 7 days before the first dose of study treatment;
11. For women of childbearing potential who are sexually active, agreement to use a highly effective, non-hormonal form of contraception during and for at least 6 months after completion of study treatment; OR, a fertile male partner willing and able to use effective non-hormonal means of contraception (barrier method of contraception in conjunction with spermicidal jelly, or surgical sterilization) during and for at least 6 months after completion of study treatment;
12. Adequate organ function as shown by:
  - Absolute neutrophil count  $\geq 1,000$  cells/mm^3
  - Platelet count  $\geq 100,000$  cells/mm^3
  - Hemoglobin  $\geq 9$  g/dL
  - Serum aspartate aminotransferase (AST) and ALT  $\leq 2.5$  ULN (or  $\leq 5$  if hepatic metastases are present)
  - Total serum bilirubin  $\leq 2.0 \times$  ULN (unless the subject has documented Gilbert Syndrome)
  - Alkaline phosphatase levels  $\leq 2.5 \times$  ULN ( $\leq 5 \times$  ULN in subjects with liver metastasis)
  - Serum creatinine  $\leq 2.0$  mg/dL or 177  $\mu$ mol/L
  - International normalized ratio (INR) or activated partial thromboplastin time (aPTT)  $< 1.5 \times$  ULN (unless on anticoagulant treatment at screening);
13. Able to swallow capsules;
14. Any toxicity from prior chemotherapy has resolved or is Grade 1 (NCI-CTCAE, Version 4.0).

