### 6.3 Modification of Study Investigational Product Dosing for a Subject

With the exception of elevated LFTs and hypercalcemia, both of which are further addressed below, subjects who experience an AE with Grade  $\geq 3$  intensity (NCI-CTCAE, Version 4.0) and/or intolerance may have a dose reduction from 18 mg to 9 mg per day or a drug interruption based on the medical judgment of the Investigator and after confirmation by the study Medical Monitor. The drug interruption may last for a period of up to 7 days after which the subject must be rechallenged with study drug (18 mg or 9 mg) or discontinued from the study. In the case of a dose reduction, once the AE has resolved or reduced in intensity to Grade 1, the subject may be rechallenged with 18 mg or maintained at 9 mg at the discretion of the Investigator.

For  $\geq$  Grade 3 elevations in LFTs, study drug should be held. A recheck of LFTs should be done within 48 hours. At the discretion of the investigator, study drug may be restarted at the 18mg dose or reduced to a 9mg dose when the LFTs have resolved to Grade 1 or better.

In the event of hepatotoxicity, please also refer to [Section 9.4](#) [Halting Rules](#).

In the event of  $\geq$  Grade 2 hypercalcemia, study drug should be held until hypercalcemia resolves to Grade 1 or better.

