## 7.2 Baseline

The following tests and procedures will be performed during the baseline visit (Visit 2), or results checked and confirmed:

- Eligibility criteria checked
- Review of prior/concomitant medications, including previous and current anticancer treatment
- Vital signs (heart rate, respiratory rate, temperature, blood pressure in a sitting position), if not done within the last 7 days
- ECOG performance status, if not done within the last 7 days
- Blood sampling for: hematology, biochemistry, and PSA if not done within the last 7 days; and serum lipid profile, serum hormones, and CTCs (enumeration and gene expression)
- Urine analysis, if clinically indicated
- AE collection
- Subjects will be asked to complete a QoL questionnaire
- Urine pregnancy test for premenopausal subjects (will be done at the site with a pregnancy stick test)
- First dose to subject at this visit. Subject will be given a carton box of 10 blister cards containing GTx-024
- Blood sample for pharmacokinetic assessment. The baseline blood sample should be collected before the subject is given their first dose of GTx-024. The exact time (hh:mm)

Protocol: A Phase 2 Open Label, Multi-Center, Multinational Study Investigating The Efficacy and Safety Of GTx-024 On Advanced, Androgen Receptor-Positive Triple Negative Breast Cancer (AR+ TNBC)	Compound No.: GTx-024 Author: [name]
---	---

and date of the blood sample will be recorded on the eCRF.

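### The only entry limit on calcium applies to subjects on IV bisphosphonate or denosumab, so others can qualify with raised calcium, in practice mainly Grade 1, unless the investigator excludes them

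*Combined protocol and SAP*

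**What the plan says.** Section 5.2, exclusion 14, and the matching item in the Protocol Summary exclude a subject for "Current treatment with intravenous bisphosphonate or denosumab with elevated serum calcium corrected for albumin or ionized calcium levels outside institutional normal limits at screening". It is the only eligibility criterion that uses a calcium value.

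The neighbouring provisions are:

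- **Inclusion 12** (Section 5.1) sets laboratory limits for blood counts, liver tests, creatinine and coagulation, and none for calcium.
- **Inclusion 14** concerns only earlier treatment: "Any toxicity from prior chemotherapy has resolved or is Grade 1".
- **Inclusion 8** says subjects with bone metastases should receive an IV bisphosphonate, denosumab or the investigator's preferred standard of care, "unless there is a contraindication or subject intolerance to these therapies". Section 5.1 adds: "For subjects who are normocalcemic, therapy can be initiated at the time the subject initiates study drug".
- **Exclusions 4 and 13** leave other conditions to the investigator. One example under 13 refers to "non-malignant medical illnesses that are uncontrolled".
- **Section 6.3** provides that at Grade 2 or higher "study drug should be held until hypercalcemia resolves to Grade 1 or better".
- **Section 2.3.1** reports, from an ongoing ER+/AR+ breast cancer study, hypercalcemia of clinical significance that investigators thought possibly due to 18 mg. Section 5.4.1 gives every subject 18 mg daily.

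**The concern.** The protocol treats calcium as a risk of this dose. It has its own hold rule, at a lower grade than the general one, and a Week 2 chemistry check that names calcium. Yet the entry limit covers only subjects already on calcium-lowering bone treatment and leaves out those without it. No reason is given for the split. At stake is the safety of a subject who begins 18 mg with calcium already above normal and no bone-directed drug. The point does not touch the sample size, the error rates or the primary analysis.

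**Working it through.** The check is a comparison of provisions.

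**Step 1. Who is covered if screening calcium is raised?**

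- *On IV bisphosphonate or denosumab:* excluded by criterion 14.
- *Bone metastases, not yet on either drug, no exemption:* inclusion 8 in Section 5.1 lets normocalcemic subjects start bone therapy together with study drug. This implies that the others start it first. Once on one of the two named drugs they fall under exclusion 14.
- *Bone metastases, contraindication or intolerance:* exempt under inclusion 8; exclusion 14 does not apply. No objective limit.
- *Bone metastases, another standard of care:* permitted by inclusion 8 and not named in exclusion 14. No objective limit.
- *No bone metastases and on neither drug:* inclusion 8 and exclusion 14 do not apply. No objective limit.

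The last three groups make up the gap, subject to the investigator's judgment under exclusions 4 and 13.

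**Step 2. What does the dosing rule remove?** A known value of Grade 2 or higher would lead to a hold under Section 6.3. Grade 1 is the level at which the same rule allows dosing. What is left is mainly Grade 1 calcium at the first dose in the three groups.

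**Step 3. How old can the calcium result be?** Section 7.2 asks for "Blood sampling for: hematology, biochemistry, and PSA if not done within the last 7 days", and says of dosing: "First dose to subject at this visit". Section 8.2.1 sends the Table 1 tests to a central laboratory; no turnaround is stated.

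- Baseline is Day 1. The schedule equates Week 4 with Day 28, so Week 2 is Day 14.
- The check has a window of ± 3 days: 14 − 3 = Day 11 to 14 + 3 = Day 17.
- Day 17 is 17 − 1 = 16 days after the first dose.
- If a sample taken 7 days before the first dose stands as baseline, the longest gap between scheduled calcium results is 7 + 16 = 23 days.

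This interval is the same for every subject, treated or not, so it describes monitoring and does not measure the eligibility gap. Unscheduled tests are possible at any time at the investigator's discretion, and Section 7.3 allows a Week 3 repeat.

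**The case against.** Four points on the other side deserve weight.

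*Exclusion 13 can reach these subjects.* It covers any concomitant medical condition that the investigator thinks raises risk, and its list is expressly not exhaustive. The example about non-malignant illness therefore does not put cancer-related hypercalcemia out of reach. This stands. The criterion is still discretionary and does not name calcium, while exclusion 14 shows that the sponsor did not leave calcium wholly to judgment.

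*The protocol accepts Grade 1 calcium on treatment.* A limit at the upper end of normal would exclude subjects whom the dosing rule tolerates. This also stands, as a cost of the change. But exclusion 14 already applies such a limit to treated subjects, so the change only extends it.

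*The ionized-calcium phrase might be a separate exclusion for everyone.* The reference to institutional limits suggests that local values may count, so the absence of ionized calcium from the central panel in Table 1 does not settle the meaning. The more natural reading ties both calcium phrases to current treatment. If sites can read it either way, the sentence needs rewording anyway.

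*There are other safeguards.* The Grade 2 hold, the Week 2 clinic visit and the optional Week 3 repeat all limit harm after dosing begins. None of them is an entry limit.

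A reader might also infer that untreated subjects are at higher risk than treated ones. The documents do not show this: Section 2.3.1 gives no baseline calcium, bone status or bone therapy for the affected subjects, and calls the link only possible.

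**Conclusion.** The point holds in a limited form. Followed as written, the criteria can admit subjects outside IV bisphosphonate or denosumab therapy with raised screening calcium unless the investigator excludes them by judgment. The residual gap is mainly Grade 1 calcium at the start of 18 mg. The number affected cannot be estimated from the documents and may be small.

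A reader might go further and infer that subjects with calcium at any grade would start 18 mg. The documents do not support that, because a known Grade 2 or higher value would be held.

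The conclusion rests on two assumptions: that exclusion 14 is read as tying both calcium phrases to current treatment, and that sites apply the Section 6.3 hold to a result known before the first dose. Severity: a minor safety improvement, worth making because it is cheap.

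**What to change.** In Section 5.2 and in the Protocol Summary, replace exclusion 14 with:

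> Albumin-corrected serum calcium (or ionized calcium, if measured) above the institutional upper limit of normal at screening, whether or not the subject is receiving an intravenous bisphosphonate or denosumab; or, in subjects receiving either, ionized calcium outside institutional normal limits.

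The second limb keeps the present bar on low ionized calcium in treated subjects.

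The cost is one criterion reworded in two places. Calcium and albumin are already in the Chem 14 panel (Table 1) drawn at screening, so no test is added. The downside is possibly a few more screen failures, including Grade 1 subjects whom the dosing rule would tolerate.

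The change does not shorten the 23-day longest gap between scheduled results, and it does not catch a subject who is normal at screening and raised on Day 1. When to recheck calcium during a hold, and at what dose to restart, is a separate dosing question and not part of this change.

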### **5.3 Strategies for Recruitment, Retention, and to Improve Adherence to Intervention Protocols**

No special strategies or activities will be employed for recruitment and retention.

### **5.4 Treatment Assignment Procedures**

#### **5.4.1 Randomization Procedures**

Not applicable; all subjects will receive GTx-024 at 18 mg daily.

#### **5.4.2 Masking Procedures**

Treatment will be open label.

#### **5.4.3 Reasons for Withdrawal**

Subjects are free to withdraw from the study at any time for any reason.

In addition, subjects may be withdrawn from the study by the Principal Investigator (PI) in consultation with the Medical Monitor for the following reasons:

- Unable to tolerate study treatment (AE requiring permanent discontinuation of study treatment)
- AEs that require treatment with a prohibited medication or a procedure

Protocol: A Phase 2 Open Label, Multi-Center, Multinational Study Investigating The Efficacy and Safety Of GTx-024 On Advanced, Androgen Receptor-Positive Triple Negative Breast Cancer (AR+ TNBC)	Compound No.: GTx-024 Author: [name]
---	---

- Development of any condition that may pose an additional risk to the subject or PI decision that this is in the best interest of the subject
- Pregnancy
- Sponsor's decision
- Subject unable to follow Investigators' instructions and comply with the study procedures
- Protocol deviation
- Disease progression

The clinical study report will include reasons for all subject withdrawals from treatment and from the study as well as details relevant to violations of Study Prohibitions and Concomitant Therapy.

#### 5.4.4 Handling of Withdrawals

Every effort will be made to ensure that subjects who withdraw (for whatever reason) from the study continue scheduled evaluations and participate in the follow-up evaluation. Subjects who withdraw due to an AE or SAE will be given appropriate care under medical supervision until the symptoms of any AE resolve or the subject's condition becomes stable.

Subjects who have TNBC and centrally confirmed AR+ status who are enrolled and receive study drug and go on to withdraw will not be replaced. Over-enrollment: Central laboratory confirmation of AR receptor status will not be available at the time of enrollment for most subjects. Subjects will be enrolled into the study based upon their medical history or locally confirmed TNBC AR+ hormonal status. Subjects who are later found after enrollment not to have centrally confirmed AR+ will be replaced by an over-enrolled subject in order for the correct number of eligible AR+ TNBC subjects to be included in the primary analysis. Subjects who are later found not to have centrally confirmed AR+ may, at the discretion of the Investigator, be maintained on the study based on a local finding of AR+, but these subjects will not be part of the evaluable subjects subset of the FAS. Furthermore, subjects who are enrolled but do not receive treatment will also be replaced by an evaluable over-enrolled subject and will not be part of the FAS. This may result in up to an additional 14 subjects being enrolled.

#### 5.4.5 Termination of Study

The Sponsor can stop this study at any time, for any reason. This study may be prematurely terminated if, in the opinion of the investigator or the Sponsor, there is sufficient reasonable cause to stop the study at the clinical site. Written notification, documenting the reason for study termination, will be provided to the Investigator or Sponsor by the terminating party.

Circumstances that may warrant termination include, but are not limited to:

- Determination of unexpected, significant, or unacceptable risk to subjects.

Protocol: A Phase 2 Open Label, Multi-Center, Multinational Study Investigating The Efficacy and Safety Of GTx-024 On Advanced, Androgen Receptor-Positive Triple Negative Breast Cancer (AR+ TNBC)	Compound No.: GTx-024 Author: [name]
---	---

- Insufficient adherence to protocol requirements.
- Data that are not sufficiently complete and/or evaluable.
- Plans to modify, suspend, or discontinue the development of the study drug.

If the study is prematurely terminated or suspended, the Sponsor will promptly inform the Investigators/institutions, and the regulatory authority(ies) of the termination or suspension and the reason(s) for the termination or suspension. The Institutional Review Board (IRB)/Independent Ethics Committee (IEC) will also be informed promptly and provided the reason(s) for the termination or suspension by the Sponsor or by the Investigator/institution, as specified by the applicable regulatory requirement(s).

Protocol: A Phase 2 Open Label, Multi-Center, Multinational Study Investigating The Efficacy and Safety Of GTx-024 On Advanced, Androgen Receptor-Positive Triple Negative Breast Cancer (AR+ TNBC)	Compound No.: GTx-024 Author: [name]
---	---

## 6 STUDY INTERVENTION/INVESTIGATIONAL PRODUCT

### 6.1 Study Product Description

#### 6.1.1 Acquisition

GTx-024 3.0 mg Softgels (capsules) will be supplied by GTx, Inc.

